#### 4.5. Intervention

Dialysis facilities randomized to the Intervention arm will adopt an approach of recommending that all patients who are initiating treatment with maintenance hemodialysis have a treatment session duration of at least 4.25 hours even if urea clearance and fluid removal are considered adequate with shorter treatment durations.

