# 4.7.2.2. Health-Related Quality of Life (HRQOL)

Quality of life is an important secondary outcome of the TiME Trial. The trial hypothesis is that extension of treatment time will improve hemodynamic stability during dialysis and increase solute clearance, and that these effects will lead to improvement in physical aspects of health-related quality of life. The HRQOL questionnaire used for the TiME Trial will be the KDQOL™36, a kidney disease-specific instrument that is administered by both dialysis provider organizations to all patients as part of routine practice and in accordance with the CMS requirement that quality of life be assessed at least once per year. The investigator team considered other QOL instruments and decided, based in part on logistical advantages, to use the survey that is already being administered as part of routine care delivery at the dialysis facilities.

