A major objective of the trial is to evaluate effectiveness of the intervention for the overall population of patients receiving maintenance hemodialysis rather than to evaluate efficacy of the intervention for a selected, non-representative subset. Because the randomized treatment assignment for the dialysis facility will be determined before patients are enrolled, a requirement for patient-level informed consent would likely result in important differences in the characteristics of participants in the two treatment groups (intervention patients would be those who *a priori* are interested in having longer dialysis sessions and the usual care cohort would be "all comers"). These differences would substantially undermine the objectives of the TiME Trial.

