#### **Analyses of Secondary Endpoints**

Several secondary analyses will be conducted, both to evaluate the secondary outcomes and to supplement the primary endpoint comparison. Secondary outcomes include hospitalization data collected during the follow-up period and quality of life measured every year. Generalized estimating equations (GEE) will be used to model repeated quality of life data. GEE can account for the correlation of repeated measures within subject and also the correlation of repeated measures within cluster. Hospitalization data will also be analyzed using a GEE approach assuming a Poisson distribution with an offset term to account for the length of follow-up for each participant.

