#### 4.5.2 Quality of Life

Quality of life as assessed by the Kidney Disease Quality of Life Short Form-36 (KDQOL 36™), a kidney disease specific instrument administered by both dialysis provider organizations at least once per year as part of routine practice and in accordance with CMS requirements. The KDQOL consists of five

sub-domains: SF12 physical scores, SF12 mental scores, burden of kidney diseases scores, symptoms/problems scores and effects of kidney diseases scores. For each sub-domain, the baseline measurement is determined by the average of all available measurements collected between 90 days before and 120 days after the date of the first transferred dialysis session; and the follow-up measurement is determined by the average of all available measurements collected beyond 120 days after the first transferred dialysis session; and the follow-up measurement is determined by the average of all available measurements collected beyond 120 days after the first transferred dialysis session. Changes in the KDQOL sub-domains between treatment arms will be compared using linear mixed effects models to account for participants within the same facility.

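### The KDQOL baseline takes in surveys up to 120 days after the first session, so any arm difference already present by then is subtracted from the estimated change

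*Combined protocol and SAP*

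**What the plan says.** SAP 4.5.2 takes as baseline the "average of all available measurements collected between 90 days before and 120 days after the date of the first transferred dialysis session", and as follow-up the "average of all available measurements collected beyond 120 days after the first transferred dialysis session". The analysis is of change: "Changes in the KDQOL sub-domains between treatment arms will be compared using linear mixed effects models", with clustering by facility taken into account.

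On timing, Protocol 5.3.1 states that "the randomized treatment assignment for the dialysis facility will be determined before patients are enrolled". Protocol 4.5 describes Intervention facilities as "recommending that all patients who are initiating treatment with maintenance hemodialysis have a treatment session duration of at least 4.25 hours", and no delay or run-in is described.

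Protocol 4.7.2.2 expects better hemodynamic stability during dialysis and better solute clearance to "lead to improvement in physical aspects of health-related quality of life". Protocol 6.3 says: "Generalized estimating equations (GEE) will be used to model repeated quality of life data". Neither document plans a sensitivity analysis with the baseline limited to surveys taken before the first session.

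**The concern.** A baseline should precede anything that allocation can influence. Here 120 of the 210 days in the window follow the first transferred session, in a facility whose arm is already fixed. The hypothesised mechanism works at each session, so an effect on quality of life within four months is plausible, although the documents give no onset time. Whatever arm difference exists in those surveys enters the baseline and is then subtracted.

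The other end of the contrast is also coarse. Every score after day 120 becomes one average. A participant who leaves in the first year contributes only early scores, and one who stays contributes an average over a much longer period. Calendar position within follow-up plays no part.

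Quality of life is one of two major secondary outcomes. If it shows no difference, a reader could not tell an ineffective strategy from an effect partly absorbed by the baseline definition.

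**Working it through.** **Inputs**
- Window: day -90 to day +120, so 120/210 = 57% of the days follow the first transferred session (SAP 4.5.2).
- SD of change 10, KDQOL completion 50%, detectable differences at 80% power of 1.4 (primary population) and 1.1 (extended population) (Protocol 6.2).
- 6432 patients, 4020 of them in the primary population; about 16 and 10 per facility; two-sided alpha 0.05 (Protocol 6.2).
- ICC 0.03 is stated for mortality. No quality-of-life ICC is given, so its use here is an assumption.

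**1. Reproducing the protocol's figures**

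Primary population: completers per arm = 4020 x 0.5 / 2 = 1005. Design effect = 1 + (10 - 1) x 0.03 = 1.27. Standard error = 10 x sqrt(2 x 1.27 / 1005) = 0.5027. Detectable difference = 2.8016 x 0.5027 = 1.41, against 1.4 stated.

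Extended population: 6432 x 0.5 / 2 = 1608 per arm. With 8 completers per facility the design effect is 1.21 and the detectable difference 1.09. With 16 per facility they are 1.45 and 1.19. An ICC near 0.02 with 10 and 16 per facility gives 1.36 and 1.13, which match both stated values after rounding, so I see no error in those figures.

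**2. What the window does to the contrast**

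Let d be the arm difference in the follow-up score, f the average weight of post-start surveys in the baseline, and g the share of d already present when those surveys are taken. With no arm difference before the first session:
- expected baseline difference = f x g x d
- expected difference in change = d - f x g x d = d x (1 - f x g)

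**3. Illustrative power at d = 1.4**

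Power = Phi(1.4 x (1 - f x g) / 0.5027 - 1.960).

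| f x g | Remaining difference | Power |
|---|---|---|
| 0 | 1.40 | 80% |
| 0.1 | 1.26 | 71% |
| 0.2 | 1.12 | 61% |
| 0.5 | 0.70 | 29% |

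The documents give neither f nor g. If surveys were spread evenly over the window, f would be 0.57. Then g = 0.25 leaves 1.20 points (67%), g = 0.5 leaves 1.00 (51%) and g = 1 leaves 0.60 (22%). If g = 0 the full 1.40 remains, whatever f is.

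**4. Opposite signs**

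If a score first worsened and later improved, g is negative. For example, f = 0.5 and g = -0.5 give 1.4 x (1 + 0.25) = 1.75, a contrast larger than the true later difference.

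**5. Precision if only pre-session baselines were used in a complete-case change analysis**

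If a share s of completers has such a survey, the detectable difference is 1.408 / sqrt(s): 1.99 at s = 0.5 and 2.82 at s = 0.25.

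**6. The follow-up average**

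Protocol 6.3 plans a model for repeated scores, and Protocol 6.2 expects repeated measures to lower the detectable difference further. SAP 4.5.2 replaces the repeated scores with one average per participant. SAP 4.5.4 and 4.5.5 nevertheless model slope and within-participant repetition for blood pressure and ultrafiltration rate.

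**The case against.** The strongest reply is that the loss is hypothetical. The documents give no onset time for a quality-of-life effect, and with none by day 120 the window costs nothing. This stands.

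The strategy is also a recommendation. Protocol 4.5.1 leaves the prescription to the nephrologist, and patients may decline. A reader might infer that every survey from day 0 to 120 was taken on longer sessions. The text supports only that these surveys are post-allocation. The SAP also does not say how the first transferred session relates to the start of the strategy.

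The power figures are not those of the SAP's estimator. They use the original 402-facility design, not the 256 clusters and 4250 primary-population patients of Protocol 6.2.1. They also use the SD of change to year one rather than that of averaged scores, and a mortality ICC. This stands too, and the figures are illustrative only.

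A reader might further infer that nothing addresses deaths and exits. That is not so. SAP section 5 plans inverse probability weighting, and Protocol 6.4 also plans to explore the survivor average causal effect. Neither restores the time dimension lost by averaging. Protocol 6.3 calls itself an overview and defers detail to the SAP, so the change of method is a departure to be explained, not a breach.

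Finally, pre-session surveys may be scarce, because the dialysis providers administer the questionnaire as routine care to incident patients. That limits the precision of the remedy. It also means that the present baseline could consist largely of post-start surveys.

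**Conclusion.** The point holds in a conditional form. The SAP's KDQOL baseline includes post-allocation surveys, and any arm difference in them is removed from the contrast. With early and late effects of the same sign, the contrast shrinks by f x g. With opposite signs it is enlarged.

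It would go too far to say that the analysis is certainly biased towards no difference, or that power will be any particular value. The documents fix neither f nor g, and zero loss is possible. The step from 80% to 29% power over f x g from 0 to 0.5 shows sensitivity under borrowed assumptions and is not a forecast.

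If the arms do not differ at any time, the window does not inflate type I error. The mortality endpoint is not touched. The single follow-up average is a second, separate weakness: it ignores time and leaves the protocol's repeated-measures plan without explanation. Both should be corrected, but neither threatens the trial's main conclusion.

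**What to change.** In SAP 4.5.2:
- Count as baseline only surveys dated on or before the first transferred session, and classify all later surveys as follow-up.
- Compare the arms with a longitudinal mixed model on all dated scores, with facility and participant random effects. Enter pre-session scores as responses, so that participants without one are kept.
- Retain the present window definition as a sensitivity analysis.
- State the assumptions: opt-out enrolment after known allocation is not selective by arm, and missing surveys are ignorable given the data used. Patients receive arm-specific information sheets, 10 facilities withdrew after randomization, and about 50% completion is assumed, so randomization alone does not secure these.

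Using the present window average as a covariate would not help, because allocation can affect it.

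The cost is SAP wording and a different model on data already collected. Some precision is lost if pre-session surveys are few. The complete-case figures of 1.99 and 2.82 do not apply to this model, which keeps everyone. With few true baselines, however, it approaches a comparison of follow-up scores alone, and the documents do not give the SD of those scores. Which time point to treat as the main contrast, and which score as the key one, are choices for the sponsor and not part of the correction.

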population), assuming an ICC of 0.03. With this sample size the trial will also have 80% power to detect a HR of 0.88 in the extended population with a two-sided alpha level of 0.05.

Hazard Ratio	Intra-class Correlation Coefficient	Number of Dialysis Facilities	Sample Size for Primary Assessment Population	Total Sample Size
0.9	0.04	1038	10380	16608
	0.03	970	9700	15520
	0.02	902	9000	14432
0.85	0.04	432	4320	6912
	0.03	402	4020	6432
	0.02	374	3740	5984
0.8	0.04	230	2300	3680
	0.03	216	2160	3456
	0.02	200	2000	3200

Table 2.	Sample Size	Requirement
----------	-------------	-------------

For the secondary outcome of hospitalization, a hospitalization rate of at least one per patient per year is expected. Conservatively estimating the minimum detectable effect size using only the first hospitalization, and assuming an ICC of 0.03, the study has 80% power to detect a hospitalization risk ratio of 0.90 in the primary treatment assessment population and 0.92 in the extended population. For the quality of life outcome, estimating, based on data from the HEMO trial, that the standard deviation of the change of the Physical Health Composite is approximately 10 units from baseline to year one, and assuming that 50% of the participants will complete the KDQOL™36, the study has 80% power to detect a difference of 1.4 for the change in the physical composite score (PCS) or mental composite score (MCS) in the primary efficacy population and a mean difference of 1.1 in the extended population. In repeated measures analyses, the actual minimum detectable effect size will be even smaller because quality of life will be assessed once per year during the follow-up period.

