	2. Treatment with maintenance dialysis in a participating facility.		
	3. Age ≥18 years.		
	Exclusion Criteria		
	
 
Unwillingness to participate. Patients receiving dialysis in facilities in the Intervention arm can participate without agreeing to a minimum dialysis session duration of 4.25 hours. Data collection for such participants will be identical to those who receive the session duration of ≥4.25 hours.
 
Patients who are unable to provide consent for dialysis care will be avaluated from trial participants.
 
		
Outcomes	excluded from trial participation.		
Outcomes	Primary Outcome: death Major Secondary Outcomes: hospitalizations, health-related quality of life		
Duration of intervention	Up to 3 years		
Analytic Approach	
 
Primary outcome: intention to treat comparison of time to death between Intervention and Usual Care groups.
 
		
	Analysis will include generation of the hazard ratio and 95% confidence interval for the intervention. Significance testing will be performed with two-tailed p values of ≤ 0.05 considered significant. Survival curves with 95% confidence intervals will be generated using the Kaplan-Meier method. Secondary analyses will incorporate adjustment for co-variables that are not balanced between randomization groups.		
	2. Secondary outcomes:		
	
 
a) comparison of hospitalization rates between Intervention and Usual Care groups
 
		
	
 
b) comparison of change over time in KDQOL™36 domains between Intervention and Usual Care groups
 
		
	3. Primary analysis population : patients with anthropometric volume ≤ 42.5 liters. Referred to as "Primary Treatment Assessment Population."		
	4. Secondary analysis population : all patients. Referred to as "Extended Analysis Population."		
Study Oversight	An independent Data and Safety Monitoring Board (DSMB) appointed by NIH will review trial progress, data quality, and interim analyses throughout the course of the trial in accordance with a Data and Safety Monitoring Plan.		

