#### 4 FINAL DATA ANALYSIS UPON COMPLETION OF TRIAL

#### 4.1 General Approach

Upon completion of the trial, after all data has been entered in the database and query resolution is complete, description of the data and the primary statistical analysis will be performed. The DCC will produce a final report outlining all analyses and interpretation of the results. The report will be used as the basis of the primary results manuscript to be prepared for publication. Details of the analyses and statistical methods to be included in the final report are outlined in this Statistical Analysis Plan. All statistical tests described will be conducted using a two-sided level of significance.

Before proceeding with inferential analyses, the data for this study will be fully described. Data will be examined for the primary outcome and all covariates to assess distributional assumptions, and balance of covariates among the study arms.

In this normal theory framework, we will first test for any difference between the trial arms, using a multivariable linear model. The multivariable model will be implemented where the interest is on testing the two arms using a Wald test. The assessment of the primary hypothesis of no difference between the arms will be conducted using a two-sided test.

Since randomization will be implemented at the site level, the intra-cluster correlation will be addressed in the models for all analyses. The design factors, stratification on each site's racial distribution (black vs non-black) and catheter use, not included in the primary analysis will be assessed in secondary analyses.

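### The KDQOL change-score model in SAP 4.5.2 names no covariates; adding the baseline score would gain precision at almost no cost

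*Combined protocol and SAP*

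**What the plan says.** Health-related quality of life is a major secondary outcome in both documents. The SAP's Protocol Summary describes it as a "comparison of change over time in KDQOL" 36 domains between the arms.

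SAP 4.5.2 defines the baseline for each of the five sub-domains as the "average of all available measurements collected between 90 days before and 120 days after the date of the first transferred dialysis session". The follow-up value is the average of everything collected after that window. The analysis is then: "Changes in the KDQOL sub-domains between treatment arms will be compared using linear mixed effects models to account for participants within the same facility". The only stated purpose of the model is to handle facility clustering.

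SAP 4.1 says in general terms that "we will first test for any difference between the trial arms, using a multivariable linear model", without listing what the model contains. Protocol 6.3 (Analyses of Secondary Endpoints) names a different method: "Generalized estimating equations (GEE) will be used to model repeated quality of life data". It does not mention the baseline score as a covariate either.

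The power statement in Protocol 6.2 takes it that "the standard deviation of the change of the Physical Health Composite is approximately 10 units from baseline to year one", "assuming that 50% of the participants will complete the KDQOL" 36, and reports 80% power for a difference of 1.4 in the primary population.

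**The concern.** Subtracting the baseline fixes its regression slope at 1. When the two scores have similar SDs, the least-squares slope is about rho, which is below 1. Two things follow.

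- **Precision.** The change score carries more variance than a model that estimates the slope, so a powered major secondary outcome is tested less sharply than the collected data allow.
- **Entry imbalance.** If the arms happen to differ at entry, the change score over-corrects. The arm that starts lower shows an apparent gain through regression to the mean.

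Some features of the design make an entry difference in the analysed set worth guarding against. Facilities are allocated before patients enrol, the information sheets differ by arm, ten facilities withdrew after randomisation, and only half of participants are assumed to complete the questionnaire.

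**Working it through.** **Inputs from Protocol 6.2.** 4020 patients in the primary population, 402 facilities with about 10 such patients each, 50% completion, SD of change 10. Allocation is 1:1 (Protocol 4.4) and alpha is 0.05 two-sided.

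**Assumed, because the documents do not give them.** An ICC of 0.03 for KDQOL (6.2 states 0.03 for mortality and hospitalization only), equal SDs at baseline and follow-up, and the correlation rho, shown as a range.

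**Step 1: reproduce the plan's figure.**
- Completers: 4020 × 0.5 = 2010.
- Design effect: 1 + (10 − 1) × 0.03 = 1.27.
- SE of the arm difference: sqrt(4 × 10² × 1.27 / 2010) = 0.503.
- Detectable difference at 80% power: (1.96 + 0.84) × 0.503 = 1.41, against the stated 1.4. Power at exactly 1.4 is 79.5%.

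The reproduction uses 10 patients per facility in the design effect. With the 5 expected completers per facility instead, power at 1.4 would be 84.3%.

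**Step 2: variance ratio.** With common score variance s²:
- Var(change) = 2s²(1 − rho)
- Var(baseline-adjusted) = s²(1 − rho²)
- Ratio = (1 + rho)/2

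**Step 3: power after adjustment.** Starting from 80%, power = Phi(2.80/sqrt(ratio) − 1.96). The second power column assumes that the covariate lowers only within-facility variance. In units of total variance, a facility mean has variance 0.03 + 0.97/10 = 0.127, so the ratio becomes (0.097 × (1 + rho)/2 + 0.03)/0.127.

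| rho | ratio | power | detectable difference | within-facility ratio | power |
|---|---|---|---|---|---|
| 0.4 | 0.70 | 91.8% | 1.18 | 0.771 | 89.1% |
| 0.5 | 0.75 | 89.9% | 1.22 | 0.809 | 87.6% |
| 0.6 | 0.80 | 88.0% | 1.26 | 0.847 | 86.1% |
| 0.7 | 0.85 | 86.0% | 1.30 | 0.885 | 84.6% |
| 0.8 | 0.90 | 84.0% | 1.34 | 0.924 | 83.0% |

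An SD of change of 10 implies rho = 0.5 only if the score SD is also 10, since 2 × 100 × (1 − 0.5) = 100. The documents do not give the score SD.

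**Step 4: entry imbalance.** If the arms differ by d at baseline, the expected change contrast moves by −(1 − rho)d. Per point this is 0.5 at rho 0.5, 0.4 at 0.6 and 0.2 at 0.8, against a detectable difference of 1.4.

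**Step 5: early effect inside the baseline window.** Let B be a treatment effect already present in the baseline average and F the effect at follow-up. The change score estimates F − B. The adjusted model estimates about F − rho × B, so it removes less.

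**Step 6: current design.** Protocol 6.2.1 moves to 256 facilities and 4250 patients, about 16.6 per facility, but does not redo the quality-of-life power. With 2125 completers and ICC 0.03, the detectable change-score difference is 1.47 using 16.6 per facility (design effect 1.468), or 1.34 using 8.3 (design effect 1.219). The ratio (1 + rho)/2 does not depend on the number of facilities; the within-facility ratio does.

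**The case against.** **The plan does not exclude adjustment.** A reader might infer that the SAP rules the baseline covariate out. It does not. SAP 4.5.2 is silent, and the general wording in SAP 4.1 could be stretched to include it. This stands: the accurate statement is that no covariates are specified. But the documents do say so when adjustment is meant, as for mortality (Protocol 6.3) and first hospitalization (SAP 4.5.1), and leaving the model open until data are seen is no better.

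**There is no power shortfall.** A reader might infer that the quality-of-life comparison is underpowered. The outcome, the power calculation and the analysis all concern change and agree with each other, so the stated 80% holds on the plan's own terms. What is lost is power that could have been had.

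**No single figure for the gain is supported.** A gain of about 10 points needs rho 0.5; at rho 0.8 it is about 4. The documents give no rho, so only the range can be reported.

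**The change score is not biased as such.** Over randomisation it is unbiased. With SD 10 and the same design effect, the baseline difference also has an SE of about 0.503, so a 1-point chance imbalance is about two SEs. A 0.5-point imbalance shifts the contrast by only 0.25 at rho 0.5. The consent waiver and opt-out are meant to limit selection (Protocol 5.3.1), and nothing in the documents shows that entry scores differ. If selection were systematic, covariate adjustment would not cure all of it.

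**The baseline window reaches day 120.** Baseline may therefore contain some treatment effect. That is a separate weakness and does not favour the change score (Step 5). It does count against a longitudinal model that forces a common baseline mean across arms, as does enrolment after open-label allocation.

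**Conclusion.** The point holds as a nearly free improvement to a secondary analysis. SAP 4.5.2 uses the baseline score only by subtraction and names no covariates. Under equal SDs, ICC 0.03 and the 402-facility design, adjustment would raise power at 1.4 points from 80% to between 84% (rho 0.8) and 90% (rho 0.5). If only within-facility variance falls, the result is about 2 points lower at rho 0.5 to 0.6 and about 1 point lower at rho 0.7 to 0.8. The direction is secure for any rho below 1 under equal SDs; the size rests on assumptions that the documents do not supply. Protection against entry imbalance is a second benefit, conditional on such an imbalance occurring.

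**What to change.** In SAP 4.5.2, model the follow-up sub-domain score on arm, with the baseline sub-domain score as a covariate and a facility random effect. Report the change-score comparison as supportive. Align Protocol 6.3, which plans GEE on repeated scores, so that both documents name one quality-of-life method with the same baseline term. A constrained longitudinal model with a common baseline mean should be at most a sensitivity analysis.

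The cost is a line of SAP text and the matching protocol wording. The same participants and data are used, since a change score already requires a baseline. With the present baseline window, the adjusted model removes less of any early effect than the change score does.
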